#### **Prior/Concurrent Therapy or Clinical Trial Experience**

- [29] Have received cDMARDs and/or other therapies such as, but not limited to: gold salts, cyclosporine, azathioprine, dapsone, 6-mercaptopurine, mycophenolate mofetil, or any other immunosuppressive agents within 4 weeks prior to baseline randomization.

Exception: MTX (oral or parenteral up to 25 mg/week), sulfasalazine (up to 3 g/day), or hydroxychloroquine (up to 400 mg/day) may be allowed IF at stable dose for at least 4 weeks prior to baseline randomization

AND

if used, must not be in any combination with other cDMARDs.

Note: If MTX is used, local standard of care is to be followed for concomitant administration of folic or folinic acid with MTX.

- [30] Use of oral corticosteroids  $>10$  mg/day prednisone or its equivalent.

**Note:** If patients are taking prednisone or its equivalent and the dose is  $\leq 10$  mg/day, the dose must be stable for at least 4 weeks prior to baseline randomization.

- [31] Have received any prior, or are currently receiving, treatment with biologic or other immunomodulatory agents, including investigational therapies (such as but not limited to Janus kinase (JAK) inhibitors, IL-1, IL-6, IL-23, IL-17 [including ixekizumab], IL-17R, T cell, or B cell targeted therapies).

Note: Previous TNF inhibitor therapy is permitted.

- [32] Are currently enrolled in, have participated, or discontinued from a clinical trial involving an investigational product or nonapproved use of a drug or device within the last 30 days prior to screening or a period of at least 5 half-lives of the last administration of the drug, whichever is longer.

**Note:** Investigational products that are biologic or other immunomodulatory agents are not permitted, regardless of washout period (described in criterion above).

- [33] Are currently enrolled in any other clinical trial involving an investigational product or any other type of medical research judged not to be scientifically or medically compatible with this study.
- [34] Are currently receiving or have received treatment with denosumab within 6 months prior to baseline randomization.
- [35] Have received any parenteral glucocorticoid administered by intra-articular, intramuscular, or IV injection within 6 weeks prior to baseline randomization, or for whom a parenteral injection of glucocorticosteroids is anticipated during the Blinded Treatment Dosing Period (Period 2) of the study.

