### **Conventional DMARDs:**

#### Blinded Treatment Dosing Period (Period 2):

Discontinuation of excluded oral or injectable cDMARDs before study enrollment must occur at least 4 weeks prior to baseline. Methotrexate (oral or parenteral up to 25 mg/week), sulfasalazine (up to 3 g/day), or hydroxychloroquine (up to 400 mg/day) may be allowed IF at stable dose for at least 4 weeks prior to baseline randomization.

During Period 2, alteration of cDMARD dose or route, and/or introduction of a new cDMARD, are not permitted, unless required for safety reasons. Conventional DMARDs can only be used as single agents and not in combination with other cDMARDs. If, at any time, the investigator believes that side effects or laboratory abnormalities may be attributable to the cDMARD, the cDMARD dose is to be lowered or the medication stopped.

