[23] Have a known immunodeficiency or are immunocompromised to an extent such that participation in the study would pose an unacceptable risk to the patient	Do not exclude from PPS	Monitor
[24] Have or had a herpes zoster or any other clinically apparent varicella-zoster virus infection within 12 weeks of V2	Do not exclude from PPS	Monitor
[25] Have any other active or recent infection within 4 weeks of V2 that would pose an unacceptable risk to the patient	Do not exclude from PPS	Monitor
[26] Have a known allergy or hypersensitivity to any biologic therapy that would pose an unacceptable risk to the patient if participating in this study	Exclude from PPS	Monitor
[27] Have had surgical treatment of a joint to be assessed in the study within 8 weeks before	Exclude from PPS depending on the clinical	Monitor

Important Protocol Deviation Category/Subcategory/Study Specific	Action for PPS Analysis	Source to Identify Protocol Deviation^a
baseline randomization or will require such during the first 16 weeks of the trial	significance	
[28] Had any major surgery within 8 weeks before V2, or will require such during the study that would pose an unacceptable risk to the patient	Do not exclude from PPS	Monitor
[29] Have received cDMARDs, and/or other therapies such as but not limited to: gold salts, cyclosporine, azathioprine, dapsone, 6-mercaptopurine, mycophenolate mofetil, or any other immunosuppressive agents within 4 weeks before baseline randomization.	Exclude from PPS 
 1. Stopped or decreased dose for a current one ≤ 3 days before randomization; or 2. Start new treatment or increased dose for current one or started a new one < 4 weeks before randomization. 	Monitor and Stats
[30] Current use of oral corticosteroids > 10 mg/day prednisone or its equivalent	Exclude from PPS 
 1. If dose > 10mg/day any time within 4 weeks; or 2. Stopped or decreased dose for a current one < 10 days before randomization; or 3. Start new treatment or increased dose for current one or started a new one < 4 weeks before randomization; 	Monitor and Stats
[31] Have received any prior, or are currently receiving, treatment with biologic or other immunomodulatory agents, including investigational therapies (such as but not limited to Janus kinase (JAK) inhibitors, IL-1, IL-6, IL-23, IL-17 (including ixekizumab), IL-17R, T cell, or B cell targeted therapies)	Exclude from PPS	Monitor and Stats

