[32] Are currently enrolled in, have participated, or discontinued from a clinical trial involving an investigational product (IP) or nonapproved use of a drug or device within the last 30 days before screening or a period of at least 5 half-lives of the last administration of the drug, whichever is longer; for Brazil patients, patients completed a clinical trial involving an IP or nonapproved use of drug or device unless there is direct benefit to patient	Exclude from PPS	Monitor
[33] Are currently (for all sites except Brazil sites) or concurrently (for Brazil sites, unless	Exclude from PPS	Monitor

Important Protocol Deviation Category/Subcategory/Study Specific	Action for PPS Analysis	Source to Identify Protocol Deviation^a
there is direct benefit to patient) enrolled in any other clinical trial involving an investigational product or any other type of medical research judged not to be scientifically or medically compatible with this study		
[34] Are currently receiving or have received treatment with denosumab within 6 months before baseline randomization	Do not exclude from PPS	Monitor and Stats
[35] Have received any parenteral glucocorticoid administered by intra-articular, intramuscular, or IV injection within 6 weeks before baseline randomization, or a parenteral injection of glucocorticosteroids is anticipated during the Period 2	Exclude from PPS	Monitor and Stats
[36] Use of any opiate analgesic at average daily doses >30 mg/day of morphine or its equivalent or use of variable doses of any opiate analgesic within 6 weeks before baseline randomization.	Exclude from PPS 1. If doses >30 mg/day any time within 6 weeks before randomization; or 2. Stopped or decreased dose for a current one <7 days before randomization; 3. Start new treatment or increased dose for current one or started a new one <6 weeks before randomization.	Monitor and Stats
[37] Had a live vaccination or participated in a vaccine clinical study within 12 weeks before V2, or intend to have a live vaccination during the study or within 12 weeks of completing study treatment	Do not exclude from PPS	Monitor
[38] Had a vaccination with BCG within 12 months before V2, or intend to have this vaccination with BCG during the study or within 12 months of completing study treatment	Do not exclude from PPS	Monitor and Stats
[39] Have a body temperature $\geq 38^{\circ}\text{C}$ (100.5°F) at V2	Do not exclude from PPS	Monitor and Stats

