Sub-Category: Excluded Con-meds	Exclude from PPS (Excluded Con-meds refers to clinically meaningful change in con-meds [Appendix 13] when occurred during Period 2 and prescribed for primary study condition) Excluded Con-meds in Period 3 refer to the lists in Appendix 13 .	Monitor and Stats
Sub-Category: Lab/Imaging Criteria		
Missing imaging as per protocol schedule of events	Do not exclude from PPS	Monitor
Missing lab chemistry and hematology: missing baseline or not having at least 1 postbaseline	Do not exclude from PPS	Stats
Sub-Category: Other		
Missing QIDS total score: missing baseline or any scheduled visit before discontinuation visit	Do not exclude from PPS	Stats
Missing Columbia scale at any visit except V1	Do not exclude from PPS	Monitor and Stats
Missing ASAS components for ASAS40 derivation: not having Week 16 measurement for patients who have completed Week 16	Do not exclude from PPS. Note: if missing ASAS components lead to missing ASAS40, such patient will be treated as nonresponder for the Week 16 ITT analyses	Stats
Had unqualified site personnel perform clinical safety and/or efficacy assessments	Do not exclude from PPS	Monitor
Category: Investigational Product		
Sub-Category: Treatment Assignment/Randomization Error		
Took incorrect study medication	Do not exclude from PPS. Analyze ‘As randomized’ or ‘As assigned’.	Monitor and Stats
Sub-Category: Compliance	Exclude from PPS when occurred during Period 2	Stats

Important Protocol Deviation Category/Subcategory/Study Specific	Action for PPS Analysis	Source to Identify Protocol Deviation ^a
Sub-Category: Patient took medication not fit for use	Do not exclude from PPS	Monitor
Sub-Category: Unblinding	Exclude from PPS	Monitor
Sub-Category: Other		
Randomized but did not take any study medication	Exclude from PPS	Stats
Category: Safety		
Sub-Category: SAEs	Do not exclude from PPS	Monitor
Category: Informed Consent		
Sub-Category: Informed Consent not Obtained/Missing/Late	Exclude from PPS	Monitor and Stats
Subcategory: Improper Informed Consent	Do not exclude from PPS	Monitor
Category: Administrative/Oversight		
Sub-Category: Reg/Ethic Approvals	Exclude from PPS	Monitor
Sub-Category: Other		
Enrolled in a site with significant GCP non-compliance issue	Exclude from PPS	Monitor

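### The per-protocol rule for exclusion [29] tests recent starts, stops and dose changes but, on its most natural reading, not receipt of the prohibited treatment itself

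*SAP*

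**What the plan says.** Protocol Section 5.2, criterion [29], is about receipt. Its list of barred treatments starts with cDMARDs and ends with "mycophenolate mofetil, or any other immunosuppressive agents within 4 weeks prior to baseline randomization". The exception covers methotrexate (up to 25 mg/week), sulfasalazine (up to 3 g/day) and hydroxychloroquine (up to 400 mg/day), each at a dose stable for at least 4 weeks, and adds that the drug, "if used, must not be in any combination with other cDMARDs". Protocol Section 6.8 repeats the washout: "Discontinuation of excluded oral or injectable cDMARDs before study enrollment must occur at least 4 weeks prior to baseline".

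SAP Section 6.14, Table RHBW.6.12, sets the PPS action for each deviation. The label of row [29] repeats the barred list but leaves out the exception. The action is exclusion from the PPS, followed by two numbered conditions:

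1. "Stopped or decreased dose for a current one", with a limit of 3 days or less before randomization; or
2. "Start new treatment or increased dose for current one or started a new one", with a limit of less than 4 weeks before randomization.

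Rows [30] (oral corticosteroids) and [36] (opiates) have the same layout, but each puts the prohibited exposure first. Row [30] begins with a dose above 10 mg/day "any time within 4 weeks", and row [36] with doses above 30 mg/day "any time within 6 weeks before randomization". Row [35] (parenteral glucocorticoid within 6 weeks) excludes without conditions.

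**The concern.** The protocol asks whether a barred drug was taken in the window. The two SAP conditions ask whether a dose changed near randomization. That second test suits the stability requirement for the permitted single agents, but it does not detect the main breach of [29].

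SAP Section 6.1.5 builds the PPS from deviations that affect the primary efficacy endpoint. Section 6.10.3 uses it to support the primary ASAS40 analysis, and Table RHBW.6.5 applies it to ASAS20 as well. If patients on prohibited background immunosuppression, or recently withdrawn from it, stay in the set, agreement between the PPS and ITT results gives less reassurance on this deviation than it appears to.

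**Working it through.** The plan gives no figure for this point, so the check applies the two row [29] conditions, taken as the complete list, to patients who breach protocol [29].

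| Patient | Breaches protocol [29]? | Condition 1 (stop or decrease, ≤3 days) | Condition 2 (start or increase, <4 weeks) | PPS |
|---|---|---|---|---|
| Azathioprine, unchanged for a year and continuing | Yes | No | No | Kept |
| Methotrexate plus sulfasalazine, both stable | Yes (combination) | No | No | Kept |
| Permitted agent, stable, above its cap | Yes | No | No | Kept |
| Cyclosporine stopped on day 10 before randomization | Yes | No | No | Kept |
| Cyclosporine stopped on day 2 before randomization | Yes | Yes | No | Removed |
| Methotrexate alone, stable, within the cap | No | No | No | Kept, correctly |

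**Day count for stops.** Take the window as days 0 to 27 before randomization, which is 28 days. Condition 1 removes stops on days 0 to 3 (4 days). Stops on days 4 to 27 are kept: 28 − 4 = 24 days, and 24/28 = 86%. If the window includes day 28, the count is 25 of 29 days, again 86%.

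**Effect of one patient.** Let an arm have n patients and response rate p. Removing one responder changes the rate by −(1 − p)/(n − 1); removing one nonresponder changes it by +p/(n − 1). Use n = 100 and the rates assumed in the Protocol Synopsis, 27% (Q2W) and 7% (placebo):

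- Q2W: −0.73/99 = −0.74 points for a responder; +0.27/99 = +0.27 points for a nonresponder.
- Placebo: −0.93/99 = −0.94 points for a responder; +0.07/99 = +0.07 points for a nonresponder.

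Each misclassified patient therefore moves an arm's rate by less than about 1 percentage point, or slightly more if the PPS arm is smaller than 100.

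**Other rows that might catch these patients.** The Excluded Con-meds row refers to "clinically meaningful change in con-meds" occurring during Period 2 and prescribed for the study condition. Stable use and a stop before baseline are not such changes. Row [31] excludes unconditionally for biologic or other immunomodulatory agents, but it bars any prior use. Reading conventional immunosuppressants into it would leave the 4-week window in [29] with nothing to do.

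**The case against.** The strongest reply is that row [29] does not say its list is exhaustive. Row [7] has an explicit limiting word before its conditions and row [29] has none. One could read row [29] as removing every breach of the criterion, with the two conditions defining instability for the permitted agents. This stands in part: the exhaustive reading is the most natural because [30] and [36] share the layout and still spell out the core breach, but it is not the only one. The blanket reading has its own fault. The row label names cDMARDs without the exception, so taken literally it would remove patients on permitted stable methotrexate, sulfasalazine or hydroxychloroquine. It gives the right result only if the reader supplies the protocol's exception from outside the row.

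A second reply is that the working rule may lie elsewhere. Row [29] is identified by both monitors and programming, the detailed specification is in a separate dataset document, and the content of Appendix 13 is not readable. That limits what can be said about what was programmed. It does not repair the text of the row.

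A third reply is that the PPS deliberately uses only a subset of deviations, and Protocol Section 2.1 says axSpA responds poorly to cDMARDs. A rule aimed at changes near baseline could then be intended, and the effect of stable cDMARD use on response may well be modest. But the SAP put [29] in the subset, gives no reason for a narrow rule, and would drop a stop on day 3 while keeping uninterrupted prohibited use.

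Finally, such patients are ineligible and waivers are not permitted, so they should be few. Section 6.14 still counts important deviations by arm and lists them by patient. All of this stands.

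**Conclusion.** Row [29] does not match protocol [29] on either plain reading. Read as exhaustive, it keeps patients whose receipt of treatment is itself the breach; read as blanket exclusion, it takes in patients the protocol allows. This is worth correcting, but it concerns a supportive analysis outside the multiplicity procedure. The ITT primary analysis does not depend on it.

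A reader might infer three stronger things, and the documents support none of them:

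- **That prohibited-treatment patients were in fact retained.** The wording permits more than one reading, and the programming specification is not available.
- **That 86% of [29] deviators stay in the PPS.** The figure is a share of calendar days on which a stop could fall. It says nothing about how many patients stopped, or when. The number of deviators is not given and may be small or zero.
- **That the PPS result is biased in a known direction.** That would need counts and responses by arm, which are not given.

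The conclusion rests on the visible text of the SAP table and on reading row [29] in parallel with [30] and [36].

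**What to change.** Reconcile row [29] with protocol [29]. Add a first condition, parallel to those in [30] and [36]: exclude from the PPS any patient who, at any time in the 4 weeks before randomization, received an agent, combination or dose not covered by the protocol's own exception. Keep the two existing conditions, stated as applying to the permitted single agents. Referring to the protocol's exception brings in the single-agent requirement and the dose caps without restating them.

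The sponsor should also say which reading was programmed and report the number of [29] deviators in the PPS by arm.

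The cost is one table row and its programming, from concomitant-medication data already recorded; the PPS may lose a few patients. Timing matters. SAP Section 3 places Version 3 before the first unblinding in June 2018, and Version 4 was approved on 28 February 2019, ahead of the Week 52 lock. The Week 16 data had been unblinded by then, so any rerun of the ASAS40 and ASAS20 PPS analyses under the revised row should be labelled post hoc and shown beside the analysis under the existing rule.

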#### **9.2.4. Analysis Populations**

The following analysis populations will be used:

**Intent-to-Treat Population (ITT):** Unless otherwise specified, efficacy and health outcomes analyses for Period 2 will be conducted on the ITT population, defined as all randomized patients, even if the patient does not take the assigned treatment, does not receive the correct treatment, or otherwise does not follow the protocol. Patients will be analyzed according to the treatment to which they were assigned.

**Per-Protocol Set (PPS):** In addition, the primary efficacy analysis will be repeated using the PPS, which is defined as all randomized patients who are compliant with therapy, who do not have significant protocol deviations, and whose investigator site does not have significant GCP issues that require a report to the regulatory agencies prior to Week 16 (Visit 8). Compliance with therapy is defined to be missing no more than 20% of expected doses, not missing 2 consecutive doses (all injections at a visit are counted as 1 dose), and not have any occurrence of double-dosing (that is, took more injections at the same time point than specified in the protocol) during Period 2.

Significant protocol deviations will be described in the SAP. Patients will be analyzed according to the treatment to which they were assigned.

**Safety Population:** Safety analyses for Period 2 will be conducted on the Safety Population, defined as all randomized patients who received at least 1 dose of study treatment. Patients will be analyzed according to the treatment to which they were assigned in that period.

**Extended Treatment Period Population:** Efficacy, health outcomes, and safety analyses for Period 3 will be conducted on the Extended Treatment Period Population, defined as all patients who received at least 1 dose of ixekizumab treatment during Period 3.

**Follow-Up Population:** Safety analyses for Period 4 will be conducted on the Follow-Up Population, defined as all randomized patients who received at least 1 dose of study treatment and have entered Period 4. Patients will be analyzed according to the treatment they received before entering Period 4.

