NSAID	nonsteroidal anti-inflammatory drug
PK/PD	pharmacokinetics/pharmacodynamics
PPS	per-protocol set: The set of data generated by the subset of patients who sufficiently complied with the protocol to ensure that these data would be likely to exhibit the effects of treatment, according to the underlying scientific model.
Q2W	every 2 weeks
Q4W	every 4 weeks
rad-axSpA	radiographic axial spondyloarthritis: a subset of axSpA in which there is evidence of disease features on radiographic imaging
SAE	serious adverse event
SAP	statistical analysis plan
screen	The act of determining if an individual meets minimum requirements to become part of a pool of potential candidates for participation in a clinical study.
SF-36 MCS	Short Form 36 mental component score
SF-36 PCS	Short Form 36 physical component score
SIJ	sacroiliac joints
SpA	spondyloarthritis
SPARCC	Spondyloarthritis Research Consortium of Canada
TEAE	treatment-emergent adverse event: Any untoward medical occurrence that either occurs or worsens at any time after treatment baseline and that does not necessarily have to have a causal relationship with this treatment.
TNFi	tumor necrosis factor inhibitor

---

Term	Definition
ULN	upper limit of normal
WPAI-SpA	Work Productivity Activity Impairment–Spondyloarthritis

---

---

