6.1.5. Analysis Populations

The following major analysis populations will be used (additional analysis populations for specific analysis will be defined in the corresponding analysis section):

Intent-to-Treat Population (ITT Population): Unless otherwise specified, efficacy and health outcomes analyses for Period 2 will be conducted on the ITT Population, defined as all randomized patients, even if the patient does not take the assigned treatment, does not receive the correct treatment, or otherwise does not follow the protocol. Patients will be analyzed according to the treatment to which they were assigned.

Per-Protocol Set (PPS): In addition, the primary efficacy analysis will be repeated using the PPS, which is defined as all randomized patients who do not have a subset of important protocol deviations that impact the primary efficacy endpoint (Section 6.14). For example, patients who are not compliant with therapy during the double-blind period will be excluded from the PPS. Compliance with therapy is defined to be missing no more than 20% of expected doses, not missing 2 consecutive doses (all injections in an injection week are counted as 1 dose), and not have any occurrence of over-dosing (that is, took more injections at the same time point than specified in the protocol) during Period 2.

Patients will be analyzed according to the treatment to which they were assigned.

Safety Population: Safety analyses for Period 2 will be conducted on the Safety Population, defined as all randomized patients who received at least 1 dose of study treatment. Patients will be analyzed according to the treatment to which they were assigned in that period.

Extended Treatment Period Population: Efficacy, health outcomes, and safety analyses for Period 3 will be conducted on the Extended Treatment Period Population, defined as all patients who received at least 1 dose of ixekizumab treatment during Period 3.

All Ixekizumab Exposures Safety Population: Safety analyses for combined Blinded Treatment Dosing Period and Extended Treatment Period will be conducted on the All Ixekizumab Exposures Safety Population, defined as all patients who received at least 1 dose of ixekizumab during the study. For each patient, only periods in which ixekizumab is administered are included.

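### The per-protocol set keeps patients who took the wrong study medication, although its own criterion and the neighbouring rows of the deviation table point to removing them; the likely effect is small

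*SAP*

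**What the plan says.** SAP Section 6.1.5 defines the PPS as "all randomized patients who do not have a subset of important protocol deviations that impact the primary efficacy endpoint" and refers to Section 6.14 for the list. Table RHBW.6.12 in that section has a row "Took incorrect study medication", under treatment assignment or randomization error. Its action is not to exclude from the PPS, followed by "Analyze ‘As randomized’ or ‘As assigned". No reason is given.

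Other rows of the table do exclude: Period 2 non-compliance, unblinding, and "Randomized but did not take any study medication". Compliance in SAP Section 6.1.5 means "missing no more than 20% of expected doses, not missing 2 consecutive doses", and no occasion with more injections than specified.

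For grouping, the SAP says of the PPS: "Patients will be analyzed according to the treatment to which they were assigned". Protocol Section 9.2.4 has the same grouping rule. It limits the PPS to compliant patients "who do not have significant protocol deviations" at sites without significant GCP issues, and leaves the list of deviations to the SAP. The glossary in Protocol Appendix 1 gives the purpose: PPS patients are those who "sufficiently complied with the protocol to ensure that these data would be likely to exhibit the effects of treatment".

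**The concern.** Receiving another arm's drug bears directly on ASAS40, since the design assumes very different response rates on Q2W and placebo. A placebo patient who in fact received ixekizumab, analysed as placebo, does not show the effect of placebo. The ITT definition already takes in patients who did not receive the correct treatment. If the PPS keeps them too, it cannot show whether the primary result is sensitive to wrong dosing.

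The PPS is the named support for the primary analysis (Protocol Section 9.4.1, SAP Section 6.10.3) and is also used for ASAS20. Retained swaps between active and placebo pull its estimate towards no difference. That weakens it as a check.

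**Working it through.** **1. The rows side by side (SAP Table RHBW.6.12)**

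| Deviation | PPS action |
|---|---|
| Took no study medication | Exclude |
| Non-compliant in Period 2 | Exclude |
| Unblinded | Exclude |
| Took incorrect study medication | Keep, in the randomized arm |

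A patient with no drug at all is removed, while one given the other arm's drug throughout is kept. The as-assigned sentence does not settle this: it says in which arm a PPS patient counts, not who belongs to the PPS.

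**2. Does the compliance rule catch the error?**

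Period 2 dosing falls at Weeks 0, 2, 4, 6, 8, 10, 12 and 14. That is 8 doses, because all injections in one injection week count as one dose. It is 9 injections in total (SAP Section 6.8).

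- One missed dose: 1/8 = 12.5%, compliant.
- Two missed doses: 2/8 = 25%, above 20%, excluded.
- Nine wrong syringes taken on schedule: 9/9 = 100% administered, none missed, none extra, so compliant.

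The rule counts injections and does not look at content.

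**3. The plan's own figure**

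Inputs from the Protocol Synopsis: 100 per arm, ASAS40 of 27% (Q2W) and 7% (placebo), two-sided Fisher's exact test at 0.05, stated power about 96%. Exact enumeration gives 96.5%; the pooled normal approximation gives 96.9%. The figure is reproduced, so these rates can be used for sizing.

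**4. Shift per patient**

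Assume that a fully swapped patient (Q2W for placebo or the reverse) responds at the other arm's planning rate.

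- Expected shift in the difference: (27 − 7)/100 = 0.2 points.
- Maximum, if the error certainly changes that patient's response status: 1/100 = 1 point.
- Three such patients: 3 × 0.2 = 0.6 points expected, 3 points at most, out of 27 − 7 = 20.

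PPS arms will be somewhat smaller than 100. With 90 (assumed), the expected shift is 20/90 = 0.22 points.

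**5. Range over an assumed frequency**

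The documents give no frequency, so m, the fraction fully swapped, is an assumption. With swaps in both arms, the expected rates are 27(1 − m) + 7m and 7(1 − m) + 27m, and their difference is 20(1 − 2m). Power is from Fisher's exact test.

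| m | Kept: difference | Kept: power, 100 per arm | Excluded: difference | Excluded: power (n per arm) |
|---|---|---|---|---|
| 1% | 19.6 | 95.7% | 20 | 96.3% (99) |
| 2% | 19.2 | 94.9% | 20 | 96.1% (98) |
| 5% | 18.0 | 91.5% | 20 | 95.5% (95) |
| 10% | 16.0 | 83.0% | 20 | 94.4% (90) |

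If only the active arm is affected and kept, the difference is 20(1 − m) = 19.8, 19.6, 19.0 and 18.0 points, with power 96.2%, 95.9%, 95.0% and 93.1%.

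**6. Would a threshold on wrongly filled doses work?**

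On the schedule in Protocol Table RHBW.2, active doses fall at all 8 occasions for Q2W and at Weeks 0, 4, 8 and 12 for Q4W.

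- Q2W and placebo swapped: 8/8 wrong, excluded.
- Q4W and placebo swapped: 4/8 = 50% wrong, excluded.
- Q2W and Q4W swapped: Weeks 2, 6, 10 and 14 wrong, 4/8 = 50%, excluded.
- One wrong dose: 1/8 = 12.5%, kept, as for one missed dose.

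**The case against.** The strongest defence is that the choice is prespecified and formally consistent. The SAP does not promise to remove every deviation that might affect ASAS40. It removes a chosen subset, and Table RHBW.6.12 is that subset. Both documents also say that PPS patients are analysed as assigned. This stands as far as it goes, so there is no conflict over grouping. A reader might infer that the two documents contradict each other on how such patients are analysed; they do not. What remains is that the subset is described by its impact on the primary endpoint, and nothing explains why wrong drug fails that test when missed drug meets it.

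Three further objections stand and limit the point.

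- The row covers everything from one wrong syringe to a whole-period swap. Excluding on any wrong syringe would be stricter than the compliance rule, which tolerates one missed dose.
- The error may be rare: Protocol Section 6.2 has site staff confirm each package number in the IWRS. Nothing in the documents supports the 5% to 10% end of the range.
- The PPS has no place in the testing procedure of SAP Section 6.5. It sits beside Fisher's exact test, categorical MMRM, placebo multiple imputation and tipping-point analyses.

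A reader might also take 1 point per patient, or 3 points for three patients, as the likely size. Those are maxima: every affected patient would have to change response status because of the error. The expected size at the planning rates is one fifth of that.

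**Conclusion.** The point holds as a minor weakness in a supportive analysis. As written, the PPS treats wrong medication as ITT does, against its stated criterion and purpose and out of line with the rows around it. At 27% v 7% and 100 per arm, each patient fully swapped between Q2W and placebo moves the expected difference by about 0.2 points towards no difference.

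This rests on three assumptions: full-period swaps, response at the other arm's planning rate, and errors unrelated to prognosis. The frequency is unknown. For mix-ups between Q2W and Q4W neither size nor direction can be computed, because the legible text gives no planning rate for Q4W.

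A reader might infer that the primary result or the 96% power is in doubt, or that efficacy could be overstated. The documents support neither. The primary analysis and the alpha-controlled tests use the ITT population, and in a superiority trial retained swaps between active and placebo make the PPS conservative.

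**What to change.** In Table RHBW.6.12, replace the blanket retention with a rule on extent. Count each wrongly filled Period 2 dose (active for placebo, placebo for scheduled active, or a Q2W/Q4W mix-up) as a dose not taken as assigned. Exclude the patient from the PPS if the existing limits are breached: more than 20% of expected doses, or 2 consecutive doses. Leave the ITT rule and the as-assigned grouping unchanged.

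Timing matters. The SAP revision history places Version 3 before the first unblinding and Version 4 (28 February 2019) ahead of the Week 52 lock, so Version 4 postdates the Week 16 unblinding that serves the primary analysis. The revised PPS should therefore be reported as a labelled sensitivity analysis beside the PPS as now specified, not in place of it.

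The cost is a few fewer PPS patients and a short programming definition. No new data are needed: the table already identifies this deviation through both monitoring and statistical programming, and SAP Section 6.12.1 already uses the dose description in the IWRS dispensing data.
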